7.7 Concomitant medication and therapy

7.7.1 Supportive care

Concomitant medications and therapies deemed necessary for the supportive care and safety of the patient should be given at the clinician's discretion as per local practice. Local supportive care includes transfusions of blood products and administration of antibiotics, analgesics, anti-pyretics and anti-emetics as necessary. G-CSF is not routinely recommended but may be administered at the investigator's discretion during the treatment of neutropenic sepsis. The use of rEPO is not recommended.

7.7.2 Other investigational agents or anti-cancer treatment

The use of other anti-cancer or investigational agents is not permitted within the trial. The concomitant use of hydroxycarbamide is permitted in patients with 'uncontrolled myeloproliferation' during the first three cycles of tefinostat therapy (see section 7.5).

7.7.3 Hepatotoxic and nephrotoxic medications

The metabolism of tefinostat is not known to be affected by CYP3A4 inducers and inhibitors. The principal route of elimination of tefinostat is hepatic metabolism. Increased creatinine has been observed at higher tefinostat doses (640mg daily). Caution is advised with potentially hepatotoxic or nephrotoxic medications; an increased frequency of monitoring is initially recommended in these patients.

8 SCHEDULE OF STUDY ASSESSMENTS

	Screening		Сус	cle 1	Сус	cle 2	Cycle 3 Cycle 4		le 4	Cycle 5		Cycle 6		;	Treatment can be	Loss of	
Week		1	1	3	5	7	9	11	13	15	17	19	21	23	25	continued as long as	response /
Day	Day -28 to 0	1	2	15	29	43	57	71	85	99	113	127	141	155	169	response is maintained - maximum follow-up interval 4 weeks	Disease progression / Intolerability
Informed consent	✓																-
Screening - eligibility criteria	✓																
Medical and CMML history	✓																
Demographic data	✓																
Concomitant medications	✓	✓			✓		✓		✓		✓		✓		✓	✓	✓
Transfusion history	✓	✓			✓		✓		✓		✓		✓		✓	✓	✓
Physical Examination	✓	✓			✓		✓		✓		✓		✓		✓	✓	✓
Vital Signs, Weight	✓	✓			✓		✓		✓		✓		✓		✓	✓	✓
Performance score (ECOG)	✓														✓		✓
Haematology	✓	✓		1	1	✓	✓	✓	✓	✓	✓	✓	✓	1	✓	✓	✓
Biochemistry	✓	✓		✓	✓	✓	✓	✓	✓	✓	✓	✓	✓	✓	✓	✓	✓
Coagulation screen	✓																
Urinalysis	✓	✓		✓	✓		✓		✓		✓		✓		✓		✓
Blood and bone marrow for central correlative studies	✓								✓						✓		
Pregnancy test (1)	✓	✓			✓		✓		✓		✓		✓		✓	✓	
ECG	✓	✓			✓		✓		✓		✓		✓			✓	
Bone marrow assessment (2)	✓								✓						✓		✓
QoL questionnaires	✓								✓						✓		
Dispensation of study medication		✓			✓		✓		✓		✓		✓		✓	✓	
Blood samples for acetylation studies (3)		✓	✓	✓	✓												
Blood samples for pharmacokinetic studies (4)		✓	✓	✓	✓												
Adverse event assessment		Monitor during treatment and for 30 days after last dose of tefinostat															
Progression / AML transformation	Monitor from day of registration to end of trial																

⁽¹⁾ Pregnancy test (urine) should be performed within 1 week of each study cycle in women of childbearing potential

⁽²⁾ Bone marrow examination should be performed at baseline, after 3 and 6 cycles of treatment and, for patients continuing beyond 6 cycles of tefinostat, at the time of stopping drug due to loss of response / disease progression or toxicity. At each of these time-points blood and bone marrow samples will be shipped for central biological correlative studies

⁽³⁾ Blood for acetylation studies will be taken pre-dose on day 1, 1hrs, 2hrs and 4hrs post dose on day 1, pre-dose on day 2, pre-dose on day 15 and pre-dose on day 29 (day 1 of cycle 2)

⁽⁴⁾ Blood for pharmacokinetic studies will be taken pre-dose on day 1, 1 hrs, 2hrs and 4hrs post dose on day 1 and pre-dose on day 2, pre-dose on day 15 and pre-dose on day 29 (day 1 of cycle 2)

The procedures to be conducted at trial visits for each subject enrolled in the study are presented in tabular form in Section 8 above and described in the text that follows.

8.1 Baseline assessments (day -28 to 0)

The following screening and baseline assessments should be performed within the period of 28 days prior to commencing the first cycle of tefinostat therapy (days -28 to 0). Some of these assessments may have been conducted as routine clinical practice prior to the patient's entry into the trial.

The following will be recorded / obtained for all patients:

8.1.1 Medical history and demographics

- Demographic details age, sex
- Past medical history to include history and treatment of past and concomitant diseases
- CMML history to include date of diagnosis, CMML subtype (at diagnosis and current), cytogenetic status at diagnosis,
 prior treatments received
- Transfusion history: red cell and platelet transfusions in the 8 weeks prior to study entry
- Concomitant medications
- ECOG performance status (Appendix 6)

8.1.2 Physical examination

- Full physical examination with particular attention to: liver and spleen size by palpation, lymph node enlargement, skin infiltration, gingival hypertrophy. (Spleen and liver measurement should be recorded in centimetres palpable below the costal margin in the mid-clavicular line, or assessed by ultrasound).
- Vital signs: pulse, blood pressure, temperature, respiratory rate, pulse oximetry
- Height and weight

8.1.3 ECG

12-lead electrocardiogram including assessment of QT_c interval

8.1.4 Pregnancy test and contraception

- A urine pregnancy test should be performed for all women of childbearing potential within 7 days prior to starting tefinostat therapy
- Female trial subjects of childbearing potential must have a negative pregnancy test and must agree to use two reliable forms of contraception during the trial and for at least 3 months after treatment has finished (Appendix 7)
- If female trial subjects are found to be pregnant this must be reported to CTR. Further information on this is in section 11.7.

- Male trial subjects must agree to use a reliable form of contraception during the trial and for at least 3 months after treatment has finished (Appendix 7)
- If a partner of male trial subject is found to be pregnant during their treatment, or within 3 months of the end of their treatment, this must be reported to CTR. Further information on this is in section 11.7

8.1.5 Haematology assessments

- Full blood count to include haemoglobin, differential white cell count (including monocyte count and blast %), platelet count, MCV
- Reticulocyte count
- Coagulation screen to include APTT, PT, fibrinogen
- Bone marrow aspiration and trephine biopsy. Analysis of bone marrow aspirate to include morphological assessment
 (with differential count), local immunophenotypic (to include blast and typical / atypical monocytoid populations) and
 cytogenetic assessments. Local assessment of trephine histology.

8.1.6 Biochemistry assessment

• Sodium, potassium, urea, creatinine (and eGFR), magnesium, calcium, phosphate, glucose, albumin, total protein, bilirubin, ALT/AST, alkaline phosphatase, LDH, uric acid

8.1.7 Urinalysis

• Using standard dipstick assessment (pH, protein, glucose, blood, ketones and leucocytes). This should be supplemented by formal quantification of any potentially-relevant abnormalities (eg. 24hr collection to quantify proteinuria).

8.1.8 Samples for central assessment and biological studies

- Separate samples of blood and bone marrow should be obtained at the time of the baseline assessment for correlative biological and biomarker studies including determination of molecular genetic profile, protein acetylation profile and hCE-1 expression level
- 4ml bone marrow and 20ml peripheral blood should be placed in EDTA tubes clearly labelled with trial number, patient initials and date of birth
- Investigators will be supplied with a collection kit which should be sent to the reference laboratory at the address below using the enhanced Royal Mail delivery service and the account reference number provide with the collection kit:

[name] Department of Haematology School of Medicine **Cardiff University** [name]

[name]

[contact]

Email: [contact]

It is also intended to store excess patient material for future research. It is mandatory to obtain the patient's specific consent to do so. For this purpose Patient Information Sheet 2 and Consent Form 2 should be used. Copies of Consent

Form 2 should be stored in the study file on site, in the patient's notes and a copy given to the patient. If a patient has

not consented to storage of excess material, the local site team should inform the CTR staff who will arrange to have

any remaining material destroyed.

8.1.9 **Quality of life assessments**

Patients should complete the EuroQol EQ5D-5L and MPN-SAF questionnaires (see Appendix 9 and 10). Completed

questionnaires should be returned to CTR using the pre-paid envelopes provided, or by scan and email.

Treatment assessments during tefinostat cycles 1-6 8.2

Each patient will receive a minimum of six 28-day cycles of tefinostat treatment, subject to tolerability. Cycles will run

continuously. During cycles 1-6 (weeks 1-24), patients will be assessed fortnightly - on day 1 and on day 15 (+/- 2 days) of each

cycle. The following will be assessed:

8.2.1 Clinical assessment (each cycle)

Adverse events (day 1 and 15)

Concomitant medications (day 1 only)

Transfusion history – at day 1 of cycle 1 this should include any transfusions administered between screening and the

start of cycle 1, for other cycles it should include any transfusions over the preceding 28 days.

Physical examination including liver and spleen size by palpation, lymph nodes, skin infiltration, gingival

hypertrophy(day 1 only)

Vital signs and weight (day 1 only)

8.2.2 Laboratory assessments (each cycle)

Full blood count to include haemoglobin, differential white cell count (including monocyte count and blast %), platelet

count, MCV (days 1 and 15)Biochemistry assessment: sodium, potassium, urea, creatinine (and eGFR), magnesium,

calcium, phosphate, glucose, albumin, total protein, bilirubin, ALT/AST, alkaline phosphatase, LDH, uric acid (days 1

and 15)

Version 3.0, 28/03/2017

Page 39 of 85

8.2.3 Pregnancy test (each cycle)

• For all women of childbearing potential a negative urine pregnancy test result should be confirmed within 7 days prior to the start each cycle of tefinostat therapy

8.2.4 Urinalysis

• Performed on days 1 and 15 (cycle 1 only), and day 1 (cycles 2-6). Using standard dipstick assessment (pH, protein, glucose, blood, ketones and leucocytes). This should be supplemented by formal quantification of any potentially-relevant abnormalities (eg. 24hr collection to quantify proteinuria).

8.2.5 Pharmacokinetic studies (cycles 1 and 2 only)

- Pharmacokinetic (PK) sampling will be performed over the initial period of tefinostat therapy.
- 2ml blood samples should be placed in Na₂EDTA/NaF vacutainers (grey top) at the following time points:

```
Cycle 1 Day 1 – pre-dose

Cycle 1 Day 1 – 1 hour post-dose

Cycle 1 Day 1 – 2 hours post dose

Cycle 1 Day 1 – 4 hours post dose

Cycle 1 Day 2 – pre-dose (24 hours post first dose)

Cycle 1 Day 15 – pre-dose
```

• At each time point, the sample will be centrifuged at 1500g for 10 minutes at 4°C in a refrigerated centrifuge. Following centrifugation, the plasma should be divided into 2 approximately equal amounts, placed into 2ml cryovials and frozen as quickly as possible to below -65°C for storage until shipment. Please refer to the Laboratory Manual for precise details of processing and shipment of PK samples.

8.2.6 Acetylation studies (cycles 1 and 2 only)

Cycle 2 Day 1 – pre-dose

- Studies of levels of histone acetylation in different haematological cell sub-populations will be performed over the initial period of tefinostat therapy
- 8ml blood samples should be placed in EDTA at the following time points:

```
Cycle 1 Day 1 – pre-dose

Cycle 1 Day 1 – 1 hour post-dose

Cycle 1 Day 1 – 2 hours post-dose

Cycle 1 Day 1 – 4 hours post-dose

Cycle 1 Day 2 – pre-dose

Cycle 1 Day 15 – pre-dose

Cycle 2 Day 1 – pre-dose
```

• Please refer to the Laboratory Manual for details of processing and shipment of histone acetylation samples

8.2.7 ECG (each cycle)

12-lead electrocardiogram including assessment of QT_c interval (day 1 only, pre-dose)

8.2.8 Bone marrow assessment (cycle 4 only)

- Bone marrow aspirate to be repeated on completion of 3 cycles of study treatment. This sample should be taken on (or within 7 days prior to) day 1 of cycle 4. Analysis to include morphological assessment (with differential count) and local immunophenotypic assessment (including blast and typical / atypical monocytoid populations).
- A bone marrow trephine biopsy is only necessary at this time point in patients for whom the baseline bone marrow aspirate sample was non-diagnostic, or in the event of an aparticulate aspirate at this time point.

8.2.9 Samples for central assessment and biological studies (cycle 4 only)

- Separate samples of blood and bone marrow should be obtained at the time of the pre-cycle 4 response assessment for central correlative biological and biomarker studies
- 4ml bone marrow and 20ml peripheral blood should be placed in EDTA tubes clearly labelled with trial number, patient
 initials and date of birth
- Investigators will be supplied with a collection kit which should be sent to the reference laboratory at the address listed in section 8.1.7 using the enhanced Royal Mail delivery service and the account reference number provide with the collection kit.

8.2.10 Quality of life assessment (cycle 4 only)

- Quality of life assessment will be repeated on day 1 of tefinostat cycle 4 (+/- 7 days)
- Patients should complete the EuroQol EQ5D-5L and MPN-SAF questionnaires (see Appendix 9 and 10). Completed
 questionnaires should be returned to CTR using the pre-paid envelopes provided.

8.3 Treatment efficacy assessment (end of cycle 6)

Patients will undergo a formal efficacy response assessment on day 29 of tefinostat cycle 6 (+/- 2 days)

8.3.1 Clinical assessment

- Adverse events
- Concomitant medications
- Transfusion history
- Physical examination including liver and spleen size by palpation, lymph nodes, skin infiltration, gingival hypertrophy
- Vital signs and weight
- ECOG performance status (Appendix 6)

8.3.2 Laboratory assessments

• Full blood count to include haemoglobin, differential white cell count (including monocyte count and blast %), platelet count, MCVBiochemistry assessment: sodium, potassium, urea, creatinine (and eGFR), magnesium, calcium, phosphate, glucose, albumin, total protein, bilirubin, ALT/AST, alkaline phosphatase, LDH, uric acid

8.3.3 Urinalysis

• Using standard dipstick assessment (pH, protein, glucose, blood, ketones and leucocytes). This should be supplemented by formal quantification of any potentially-relevant abnormalities (eg. 24hr collection to quantify proteinuria).

8.3.4 Bone marrow assessment

Bone marrow aspiration and trephine biopsy. Analysis of bone marrow aspirate to include morphological assessment
(with differential count), local immunophenotypic (to include blast and typical / atypical monocytoid populations) and
cytogenetic assessments. Local assessment of trephine histology.

8.3.5 Samples for central assessment and biological studies

- Separate samples of blood and bone marrow should be obtained at the time of the end of cycle 6 response assessment for central correlative biological and biomarker studies
- 4ml bone marrow and 20ml peripheral blood should be placed in EDTA tubes clearly labelled with trial number, patient initials and date of birth
- Investigators will be supplied with a collection kit which should be sent to the reference laboratory at the address listed in section 8.1.7 using the enhanced Royal Mail delivery service and the account reference number provide with the collection kit.

8.3.6 Quality of life questionnaire

- Quality of life assessment will be repeated on day 29 of tefinostat cycle 6 (+/- 7 days)
- Patients should complete the EuroQol EQ5D-5L and MPN-SAF questionnaires (see Appendix 9 and 10).
- Completed questionnaires should be returned promptly to CTR using the pre-paid envelopes provided, or by scan and email (the MPN-SAF Total Symptom Score forms part of the International Consortium MDS/MPN Response Criteria – see appendix 3).

Following this efficacy assessment, a short extension of tefinostat therapy (maximum 14 days) will be permitted in order to allow adequate time for sites to fully assess week 24 response assessment investigations and discuss the results with trial subjects.

'Clinical benefit' from tefinostat will be defined as:

Clinical Benefit (or better) according to International Consortium MDS/MPN Response Criteria (28) in the absence of features of disease progression

(See Appendix 3).

This definition includes 'complete remission', 'complete cytogenetic remission',' partial remission', 'bone marrow responses' or 'clinical benefit' as defined within these criteria.)

Patients who are both benefitting clinically from tefinostat and continuing to tolerate tefinostat therapy will be permitted to continue treatment, pending the availability of study drug, until there is a loss of clinical response, disease progression or the development of unacceptable toxicity. Patients who are not deemed to be obtaining clinical benefit at the time of the end of cycle 6 efficacy assessment will be taken off tefinostat therapy.

8.4 Treatment assessments for patients continuing tefinostat therapy (cycle 7 and beyond)

For patients who have a satisfactory clinical response after completion of 6 cycles and continue on trial treatment, study visits are reduced in frequency to **4-weekly** until the point of loss of response / disease progression or the occurrence of unacceptable toxicity. At each visit the following will be assessed:

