8.4.1 Clinical assessment

- Adverse events
- Concomitant medications
- Transfusion history
- Physical examination including liver and spleen size by palpation, lymph nodes, skin infiltration, gingival hypertrophy,
 cutaneous haemorrhages
- Vital signs and weight

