8.4.2 Laboratory assessments

- Full blood count to include haemoglobin, differential white cell count (including monocyte count and blast %), platelet count, MCV
- Biochemistry assessment: sodium, potassium, urea, creatinine (and eGFR), magnesium, calcium, phosphate, glucose,
 albumin, total protein, bilirubin, ALT/AST, alkaline phosphatase, LDH, uric acid

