8.5.4 Bone marrow assessment

 Bone marrow aspirate and trephine biopsy. Analysis of bone marrow aspirate to include morphological assessment (with differential count), local immunophenotypic (blast and monocytoid populations) and cytogenetic assessments.
 Local assessment of trephine histology.

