9.2 Quality of Life data collection

CMML has a heterogeneous clinical phenotype with a variable spectrum of disease-related constitutional symptoms. Previous studies of non-selective HDAC inhibitors have been associated with generalised systemic toxicities including gastrointestinal effects, fatigue and insomnia with resulting impacts on quality of life (QoL). QoL is thus an additional important outcome measure in assessing impact of tefinostat treatment in this patient population. QoL will be measured at baseline (prior to the start of treatment) and following 3 and 6 four-week cycles of tefinostat therapy. The instruments used will be the EuroQoL EQ-5D-5L (Appendix 9) and the Myeloproliferative Neoplasm (MPN) Symptom Assessment Form (MPN-SAF) (Appendix 10). The EQ-5D is a standardised instrument for use as a measure of health outcome. The EQ-5D-5L descriptive system comprises five dimensions (mobility, self-care, usual activities, pain/discomfort, anxiety /depression). The

MPN-SAF is a 27-item validated tool which aims to assess the prevalence and severity of symptoms in patients with myeloproliferative neoplasms; its use in patients with myelodysplastic/myeloproliferative neoplasms including CMML is currently being validated. The MPN-SAF Total Symptom Score is currently included within the International Consortium MDS/MPN Response Criteria on an exploratory basis. (28, 29)

Patients should be able to undertake the assessment themselves, and the local trial team are asked to facilitate this and to return the responses promptly to CTR in the pre-paid envelopes.

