10.4.2 Secondary outcome measures

- Incidence of CR / PR / clinical benefit will be defined according to the International Consortium MDS/MPN Response Criteria⁽²⁸⁾ (see Appendix 3) at day 29 of the sixth or last cycle of tefinostat (whichever is the earlier). Duration of response will be measured from the date of investigations confirming the achievement of response until the date on which it is confirmed that the patient is no longer sustaining response.
- Overall clinical response rate according to Wattel and Modified IWG criteria (see Appendix 4 and 5).
 Responses will be defined as the cumulative proportion of patients achieving minor response of better (according to Wattel criteria⁽¹⁴⁾ and/or haematological improvement or better (according to the Modified IWG criteria)⁽²³⁾ at day 29 of the sixth or last cycle of tefinostat (whichever is the earliest).
- Red blood cell transfusion independence will be deemed to have been achieved if a patient who
 received red cell transfusion support in the eight weeks prior to baseline assessment remains free
 from red cell transfusion for a period of ≥ eight weeks
- Platelet transfusion independence will be deemed to have been achieved if a patient who received
 platelet transfusion support in the eight weeks prior to baseline assessment remains free from
 platelet transfusion for a period of ≥ eight weeks
- Overall survival is defined as the time from the date of trial registration to the date of death from any
 cause. Patients discontinuing the study, lost to follow-up or still alive at the end of study will be
 censored at the date of last follow-up.
- Progression-free survival is defined as the time from date of trial registration to the date of progression
 or death from CMML. Patients who die from a cause other than CMML prior to progression will be
 censored in the analysis. The date of progression is the date of the decision to investigate a clinical
 suspicion of progression which is subsequently confirmed.
- Time to AML transformation of CMML is defined as the time from trial registration to AML transformation of CMML or last follow-up. Patients in whom CMML does not transform to AML will be censored at the last date they were known to be alive and free from AML transformation of CMML. The date of AML transformation of CMML is the date of the decision to investigate clinical suspicion of AML transformation which is subsequently confirmed.

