- Neutrophils If pre-treatment neutrophils $\leq 0.5 \times 10^9/I$: increase to $> 0.5 \times 10^9/I$ (and by $\geq 100\%$)
 - If pre-treatment neutrophils 0.5-1.0 x 10^9 /I: an absolute increase of \geq 0.5 x 10^9 /I (and by at least 50%)
- **Spleen** either a minimum 50% reduction in palpable splenomegaly of a spleen that is a least 10cm palpable at baseline or a spleen that is palpable at more than 5cm at baseline becoming not palpable
- **Symptoms** improvement in symptoms as noted by a decrease of ≥50% in the MPN-SAF Total Symptom Score (only valid if baseline score>20)*

Disease Progression (requires a combination of either 2 major, 1 major & 2 minor, or 3 minor criteria from the list below)

Major Criteria of disease progression

Increase in bone marrow blast count: -<5% blasts: ≥50% increase (and to >5% blasts)

- 5-10% blasts: ≥50% increase (and to >10% blasts)

- 10-20% blasts: ≥50% increase (and to >20% blasts)

Evidence of cytogenetic evolution: - appearance of new cytogenetic abnormality

- increase in cytogenetic burden of disease by ≥50%

• New extramedullary disease: - worsening splenomegaly (either from previously inpalpable to

>5cm palpable, or >100% increase in previous 5-10cm

splenomegaly, or ≥50% increase in previous >10cm splenomegaly)

- extramedullary disease outside the spleen (including hepatomegaly, skin lesions, granulocytic sarcoma)

Minor Criteria of disease progression

- New transfusion dependence (at least 2u of red cells in the past month for Hb<85g/l that was not associated with clinically overt bleeding or felt to be associated with therapy
- Significant loss of maximal response of cytopenias: ≥50% decrement from maximum response in neutrophils or platelets (not felt to be associated with therapy)
- Reduction in Hb by 15g/l from best response or baseline (not felt to be associated with therapy)
- Increase in symptoms as noted by an increase of ≥50% in the MPN-SAF Total Symptom Score*
- Evidence of molecular clonal evolution

^{*} The use of the MPN-SAF Total Symptom Score within the International Consortium MDS/MPN Response Criteria is currently considered exploratory. Validation among patients within MDS/MPN is currently under way. (28)

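### The MPN-SAF stops at week 24, so loss of a symptom-only response can never be measured and its duration is likely overstated; marrow-only and cytogenetic-only loss is detected only by triggered tests

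*Protocol*

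**What the plan says.** **What counts as response.** Section 8.3 accepts complete remission, complete cytogenetic remission, partial remission, marrow response or clinical benefit, and lets such patients continue until response is lost, disease progresses or toxicity is unacceptable. Under Appendix 3, clinical benefit can be met on symptoms alone: "improvement in symptoms as noted by a decrease of ≥50% in the MPN-SAF Total Symptom Score (only valid if baseline score>20" at entry to the score's valid range. An optimal marrow response does not require normal blood counts.

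**How duration is measured.** Section 10.4.2: "Duration of response will be measured from the date of investigations confirming the achievement of response until the date" on which loss of response is confirmed.

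**What is measured from cycle 7.** Section 8.4: "study visits are reduced in frequency to 4-weekly until the point of loss of response / disease progression or the occurrence of unacceptable toxicity". The content is clinical (8.4.1, including "Physical examination including liver and spleen size by palpation, lymph nodes, skin infiltration, gingival hypertrophy"), laboratory (8.4.2: "Full blood count to include haemoglobin, differential white cell count (including monocyte count and blast %), platelet count, MCV", plus biochemistry) and an ECG (8.4.3).

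**The questionnaire.** Section 9.2: "QoL will be measured at baseline (prior to the start of treatment) and following 3 and 6 four-week cycles of tefinostat therapy". The schedule table in section 8 ticks it at screening, day 85 and day 169 only. Section 8.5 does not ask for it at stopping.

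**The marrow.** It is required at baseline, after cycles 3 and 6, and, under footnote 2 of the schedule, "for patients continuing beyond 6 cycles of tefinostat, at the time of stopping drug due to loss of response / disease progression or toxicity". The stopping marrow includes "local immunophenotypic (blast and monocytoid populations) and cytogenetic assessments" (8.5.4). Section 4.3 also permits a discretionary marrow when progression is suspected or trial therapy ends early.

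**The concern.** The protocol sets a criterion for response, allows treatment to continue while that response lasts, and defines an endpoint by the date it ends. For one kind of responder it then stops collecting the measurement that would show the end. A statistical analysis plan can choose how to handle missing data, but it cannot recover questionnaires that were never given.

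Duration of response is a named secondary endpoint and will come from few patients. If the end of some responses cannot be observed, the summary mixes durations ended by measurement with durations ended by whatever handling rule is applied. The continuation condition in 8.3 has the same gap for these patients: it refers to loss of a response that is no longer measured.

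**Working it through.** The plan states no figure on this point, so the check sets the response routes beside the schedule.

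**1. Measurement after week 24, by route to response**

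| Response rests on | Scheduled from cycle 7 (8.4) | Triggered |
|---|---|---|
| Counts, transfusion, spleen | Every 4 weeks | Also at stopping (8.5) |
| Complete or partial remission | Count and organ criteria every 4 weeks; marrow not scheduled | Marrow on suspicion (4.3) or at stopping (footnote 2, 8.5.4) |
| Marrow only | None for the marrow | As above |
| Cytogenetics only | None | Cytogenetics at stopping (8.5.4); discretionary marrow (4.3) |
| Symptoms only (MPN-SAF) | None | None |

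Only the last row has neither a scheduled nor a triggered measurement.

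**2. Length of the gap.** Minimum follow-up is 18 months = 18 × 30.4375 = 547.9 days. The last MPN-SAF is at day 169. The gap is 547.9 − 169 = 378.9 days, which is 54 weeks or 13.5 four-week cycles. Over that span a continuing patient is due no MPN-SAF, no calendar marrow and no calendar cytogenetics.

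**3. What this does to a symptom-only duration.** Response can first be documented at week 12 or week 24. Section 10.4.2 gives no censoring rule for duration of response, so take two extreme assumptions for a patient who is never seen to progress or stop:
- follow only to the last MPN-SAF (week 24): 24 − 24 = 0 weeks or 24 − 12 = 12 weeks;
- treat as sustained to week 78: 78 − 24 = 54 weeks or 78 − 12 = 66 weeks.

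The difference is 54 weeks in both cases. It is decided by the handling rule and not by data.

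**4. Direction.** Onset is also recorded late, which shortens duration, but if both forms are completed the delay is at most the 12 weeks between them. The delay in recording loss has no such limit. Overstatement is therefore the likely direction, not a certain one.

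**5. Marrow-only loss: illustration on assumed values.** The protocol gives neither a rate of marrow loss nor a lag to a clinical trigger. Let T be the time from week 24 to true marrow loss, exponential with the median shown, and L the lag from silent loss to a triggered marrow, exponential with the mean shown. The recorded end is T + L. Death and end of follow-up are ignored.

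| True median T (months) | Recorded median, mean lag 1 month | Mean lag 3 months | Mean lag 6 months |
|---|---|---|---|
| 3 | 4.1 | 6.1 | 8.6 |
| 6 | 7.1 | 9.3 | 12.2 |
| 12 | 13.0 | 15.3 | 18.5 |

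The mean delay equals the assumed lag by construction. The table shows the mechanism and is not an estimate for this trial.

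**6. Number of patients.** At the 30% response rate of section 10.1, responders number 0.30 × 40 = 12. The documents do not say how many would qualify on symptoms, marrow or cytogenetics alone.

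**7. Progression.** Appendix 3 needs two major, one major and two minor, or three minor criteria. The MPN-SAF rise is one of five minor criteria and cannot be assessed after week 24. It is never sufficient alone.

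**The case against.** Much of the case on the other side stands.

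- **Marrow and cytogenetics are not absent.** A reader might infer that no test can show loss of a marrow or cytogenetic response. Section 4.3 allows a marrow on suspicion, before loss has been concluded, and footnote 2 requires one at stopping, including stopping for toxicity. What remains is that these tests need a trigger, and that loss of response is itself one of the triggers.
- **Progression-free survival does not lose its basis.** Section 10.4.2 dates progression at the decision to investigate a clinical suspicion that is later confirmed, so the endpoint is suspicion-triggered by definition. Only the one symptom criterion drops out.
- **A fall in the hazard of loss at week 24 cannot be inferred.** These responses are first seen at week 12 or 24, so at most one 12-week interval of measured risk comes before.
- **A share such as a quarter or a third of responders has no source.** No split by type of response is given.
- **The symptom score is exploratory.** Section 9.2 and Appendix 3 say so, yet the protocol still counts it towards clinical benefit.
- **Censoring rules may sit in the statistical analysis plan.** That is so, and their absence here is no fault. Censoring marrow-only responders at their last marrow would also be a poor remedy: one first documented at week 24 would get a duration of zero.
- **Avoiding repeated invasive marrows is defensible** in a disease with a median age at presentation of 75 years. That argument does not reach a questionnaire.

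**Conclusion.** The point holds for symptom-only responders who continue past cycle 6: after week 24, loss on the qualifying criterion cannot be observed at all, and the MPN-SAF progression criterion cannot be assessed. For marrow-only and cytogenetic-only responders the weaker statement holds: loss is detected only by triggered assessment and may be dated late.

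Duration of response is likely overstated for these patients. The size cannot be computed, because the documents give neither the number of such responders nor the rate of loss. What can be stated is the 54-week span without a scheduled measurement, which assumes that the patient is alive, on tefinostat and followed to the 18-month minimum.

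The consequence is limited. Duration of response is a secondary endpoint analysed descriptively (10.2). The primary response rate is read at cycle 6 or the last cycle if earlier (10.4.1), so the schedule from cycle 7 does not affect it.

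**What to change.** 1. Add the MPN-SAF to section 8.4 at an existing visit, for example every 12 weeks while on tefinostat. This keeps the spacing used up to week 24. Align section 9.2 and the schedule table.
2. Add the MPN-SAF to the stopping assessment in section 8.5.
3. Report duration of response separately for responses resting only on marrow, cytogenetic or symptom criteria, and note that loss of marrow and cytogenetic responses is detected only by triggered assessment.

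No added marrow is needed.

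**Cost.** Every 12 weeks means weeks 36, 48, 60 and 72, or four forms per patient up to week 78. If all 12 responders expected at a 30% rate continued that long, this is 12 × 4 = 48 short questionnaires, plus one at each stop. Reported durations may become shorter.
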